
4. Research Plan:

(a) Study Design and Timeframe of the Study

The study follows an experimental research plan under consideration for an award at NIH and its performance is planned for a duration of 4 years. All experiments are conducted on the Boca Raton Campus of Florida Atlantic University. The study includes a fractional factorial experimental design with repeated measurements.

(b) Research Methods

Over one or multiple days, we examine neurobehavioral processes in people controlling a robotic arm and hand to perform simple motor tasks (e.g. fragile object transportation), while a virtual peripheral nerve regeneration protocol provides users

with biologically-realistic, idiosyncratic parameters for the restoration of haptic sensation (in double-blind fashion, the cellular neurophysiologists characterizing neural regeneration with microscopy are unaware of subjects' name and condition; and the human-subject experimenters are unaware of the haptic feedback parameter that will be used in the experiment each day, which is entered by the neurophysiologist in a black-box section of the software in the case of microscopic evaluation of nerve regeneration (early part of the project), or which is automatically input by the system in the case of real time impedimentic measurements (later part of the project)). The main experimental factors are 'haptic feedback', with three modalities: full, partial (nerve-regeneration dependent) and null; and to challenge human control strategy and impose demand on haptic information, the 'transported object weight' (heavy, medium and lightweight).

Recording techniques: Subjects' electroencephalography (EEG), electromyography (EMG) and behavioral performance scores (number of drop and breakage, speed) are recorded, as well as subjective self-report (perceived task difficulty).

Other significant materials: Subjects are equipped with a soft haptic feedback armband, a cuff with variable inflation that informs of the pressure measured within the robotic hand as it manipulates objects. Subjects face a computer display (initial training session) or the robotic arm and hand (subsequent sessions).

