Procedures: After explanation of the experimental goal and signature of a written informed consent, subjects are prepared for EEG recording, an EMG array and a soft haptic feedback armband are placed on their missing (or dominant) hand. In a series of trials, they use a robotic arm and hand to perform a fragile object transportation task or various control motor actions. The task parameters are varied between trials (presence and quality of haptic feedback, weight of the visually-identical object). The task, including EEG, EMG and armband preparation, instruction and numerous breaks, and removal of the EEG electrode array, is under 2 hours. No activity is physically strenuous and subjects can ask for a break at any time. While in preliminary phases of this study, we may need to test one of more of these individual subsystems (EEG, EMG, soft actuators) independently with human subjects. Thus on the consent form we have specified this by including boxes to be checked for the combination of EEG, EMG, and soft actuators that will be evaluated during experiments.

Time commitment: Each experiment will last at most 2 hours. Subjects are free to withdraw from the study at any time with no repercussion whatsoever. At the end of each experiment, subjects are offered continued participation over the consecutive days of the week.

(c) Study Population: Subjects are 18-65y.o. volunteer with intact limbs, amputation or congenital limb absence. Inclusion criteria are normal/corrected-to-normal vision, general good health. Exclusion criteria are an amputation wound that has not yet healed, the absence of a suitable length of residual limb for placement of haptic feedback controller and EMG sensors, presence of pain that prevents utilization of those experimental appliances and the use of psychoactive drugs that modifies baseline neural activity.

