(e) Analysis Plan: We compare the neural (somatosensory neuromarkers) and behavioral characteristics (performance, subjective report) for each object weight and each feedback modality. We hypothesize that trials provided with less noisy, more accurate tactile feedback will lead to stronger and more timely somatosensory activity as measured with EEG neuromarkers, which in turn, will lead to faster and better behavioral performance while using the artificial hand. EEG analysis is conducted using the methods developed by [name] et al., PNAS, 2007. Nonparametric Mann-Whitney U-tests will be performed on the subjective evaluations and a multifactor ANOVA will be performed on the quantitative success rates related to the number of times the objects were dropped or broken, and the speed of transport. Results will be disseminated as oral and poster presentations at conference, proceedings and journal submissions.

5. Benefits: This study presents minimal risks and offers no direct health benefits to the participating subjects but aims to advance understanding on the behavioral and brain mechanisms underlying somatosensation and its plasticity. Participation in this experiment is important for society. Increased understanding on the plasticity of somatosensation will be broadly useful for behavioral neuroscience. The scientific advances expected to result from this research will specifically benefit amputees and limb-absent people who use prosthetic hands or disabled individuals who rely on robotic assistants. There are others who could benefit from this research as well, for example, doctors who perform robot-assisted surgery and their patients, or people having suffered from neurotrauma.

6. Risks: This study will involve no more risk than encountered during routine medical, psychological examination or during daily life. The EEG employed in this study is a medical grade system with optical isolation that prevents electrical risk. Sensitive EEG equipment is single-use and sterile (syringes, canula, qtips), or when not possible (EEG and EMG electrodes), decontaminated with compliant medical procedures for infectious risk. All personnel participating in this research are trained and certified by [name], who has managed EEG training at the Center for Complex Systems and Brain Sciences since 2004.

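### Section 4(e) does not say how repeated trials, sessions and participant groups enter the behavioural ANOVA, and it plans an unpaired test for ratings compared within subject

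*Combined protocol and SAP*

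**What the plan says.** Section 4(a): "The study includes a fractional factorial experimental design with repeated measurements". Section 4(b) defines the feedback factor "with three modalities: full, partial (nerve-regeneration dependent) and null", and object weight as a second factor with three levels. The Procedures paragraph makes both of them within-subject factors: "The task parameters are varied between trials (presence and quality of haptic feedback", together with object weight.

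Subjects may attend more than once: "Over one or multiple days, we examine neurobehavioral processes in people controlling a robotic arm and hand". Sessions are not all alike: "Subjects face a computer display (initial training session) or the robotic arm and hand (subsequent sessions"). The partial condition rests on "idiosyncratic parameters for the restoration of haptic sensation", and the experimenters are "unaware of the haptic feedback parameter that will be used in the experiment each day". Section 4(c) aims for three groups of 12 (control, amputee, limb absent).

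Section 4(e) compares neural markers, performance and subjective report by object weight and by feedback modality. For drops, breakages and speed, "a multifactor ANOVA will be performed on the quantitative success rates" and on speed of transport; for the subjective evaluations it names Mann-Whitney U-tests. It gives no subject, session or group term, no random effect and no error stratum. EEG follows a cited method that is not reproduced, so this point covers behavioural outcomes and ratings only.

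**The concern.** The same person supplies many trials under every modality, possibly over several days, so the observations are correlated. The modality test depends on what the ANOVA does with that correlation, and 4(e) leaves this open. Adding a subject intercept does not settle it. The nerve-dependent parameters are described as individual, so the benefit of partial feedback may differ between people, and that variation belongs in the error term for modality.

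For the ratings, a method is named and it is an independent-samples one. Perceived difficulty under two modalities comes from the same subjects, so Mann-Whitney discards the pairing.

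At stake are lost power on the success rates and ratings, and possibly too many false positives on outcomes analysed trial by trial.

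**Working it through.** **The plan's own figure.** Section 4(c) gives a minimum of seven subjects for the behavioural analysis (0.05, power 0.8). It cannot be reproduced, because no effect size, SD, sidedness or test is stated. Inverted, seven subjects at 80% power two-sided imply a standardised difference of 1.27 for a paired t-test, or 1.63 for a two-sample test with seven per group. The figure therefore does not show which kind of analysis was meant.

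**Inputs.** From the documents: 3 modalities, 3 weights, 3 × 12 = 36 subjects, alpha 0.05. Assumed: trial SD 1, skill SD σ = 0.7, session SD 0.2, subject-by-modality SD τ = 0 or 0.25, 2 trials per cell (18 per session, so 6 per modality), K = 1, 3 or 5 balanced sessions, normal outcomes.

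**Formula.** With 2 and many degrees of freedom, the 5% point of F is 2.996 and the upper tail is exp(−x). The false-positive rate is then about 0.05^(D/N), where N is the expected modality mean square with no true effect and D is the expected error mean square.

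- Single trials, no subject term: N = 1 + 6Kτ²; D = 1 + σ² + 0.2² + τ².
- Per-condition rates (each the mean of 2K trials), no subject term: N = 1/(2K) + 3τ²; D = 1/(2K) + σ² + 0.2²/K + τ².
- Subject-by-modality error term: D = N, so 5%.

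**False positives, 36 subjects.**

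| τ | K | Single trials: D/N, rate | Rates: D/N, rate |
|---|---|---|---|
| 0 | 1 | 1.53/1, 1.0% | 1.03/0.5, 0.2% |
| 0.25 | 1 | 1.5925/1.375, 3.1% | 1.0925/0.6875, 0.9% |
| 0.25 | 3 | 1.5925/2.125, 10.6% | 0.7325/0.3542, 0.2% |
| 0.25 | 5 | 1.5925/2.875, 19.0% | 0.6605/0.2875, 0.1% |

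Simulation of the same layout (4,000 runs per setting) gives 1.1, 3.1, 10.9 and 18.8% for single trials, and 0.3, 1.0, 0.2 and 0.2% for rates. With the subject-by-modality error term it gives about 5% throughout. With subject and session intercepts but no subject-by-modality term, it gives 10, 23 and 34% for K = 1, 3 and 5 at τ = 0.25.

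**Where the sign changes.** Single trials reject too often when (6K − 1)τ² > σ² + 0.2² = 0.53, that is, when τ exceeds √(0.53/5) = 0.33, √(0.53/17) = 0.18 or √(0.53/29) = 0.14 for K = 1, 3 or 5. Rates do so only when 2τ² > σ² + 0.2²/K, that is, τ above about 0.5 here.

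**Power, one session, τ = 0, full-null difference 0.3 with partial midway.** Noncentrality = 36 × 6 × (0.15² + 0.15²) = 9.72.

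- Repeated measures, F(2, 70): 0.79 (simulated 0.77 to 0.80).
- Single trials: chance that a noncentral χ² (2 df, 9.72) exceeds 5.991 × 1.53 = 9.17, which is 0.60.
- Rates: the same with 5.991 × 2.06 = 12.34, which is 0.40.

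For skill SD 0.3 to 1.0, simulated single-trial power runs from 76% down to 42%, while repeated measures stays at 78%.

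**Ratings.** Assume a within-subject correlation of 0.5. Under the null, Mann-Whitney rejects with probability about 2Φ(−1.96/√0.5) = 0.6%. Take 36 subjects, a shift of 0.5 SD and rank efficiency √(3/π) = 0.977. Signed-rank power is about Φ(0.977 × 0.5/√(1/36) − 1.96) = Φ(0.97) = 0.83. Mann-Whitney power is about Φ((0.977 × 0.5/√(2/36) − 1.96)/√0.5) = Φ(0.16) = 0.56.

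**The case against.** The strongest reply is that 4(a) announces repeated measurements and that a repeated-measures ANOVA is a multifactor ANOVA, so the intended model may be the right one. This stands to a degree. A reader might infer that the modality tests as planned use the wrong error term. The documents do not support that, because 4(e) states no error term. What remains is that the analyst must still decide on the subject-by-modality term, the place of session and the stratum for group, and these choices change the result.

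A reader might also infer a general excess of false positives. The text applies the ANOVA to success rates, and on rates the test is conservative over most of the assumed range. The inflated figures need trial-level analysis, which could apply to speed but is not stated.

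Two further inferences go beyond the text. If group were tested against trial-level error, false positives would be 65% (one session) to 91% (five), but 4(e) names no group test. If modalities were unbalanced over days, practice could bias the contrasts. An assumed gain of 0.1 to 0.2 per session and an imbalance of 0.5 to 1 session give 0.05 to 0.20. The standard error over three sessions is √(2/(18 × 36)) = 0.056, or √(2/36 × (0.0625 + 1/18)) = 0.081 with τ = 0.25. But the Procedures paragraph varies feedback between trials, and nothing says that days are unbalanced.

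On the ratings, 4(e) does not say which pairs Mann-Whitney compares, and between participant groups it would be suitable. But 4(e) lists subjective report among the outcomes compared by weight and modality, so for those comparisons the objection fails.

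**Conclusion.** The point holds as under-specification of the ANOVA, together with an unsuitable test for ratings compared within subject. It should be fixed, with medium confidence as to its practical size.

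Under the assumed SDs, ignoring subject costs power on rates (40%) and on single trials (60%) against 78%, and Mann-Whitney costs a similar amount on ratings (about 55% against 83%). For trial-level outcomes with a subject-by-modality SD of 0.25, the false-positive rate is about 10 to 20% over three to five sessions.

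Neither direction nor size is established by the documents. Every variance, the 18 trials per session and the normal outcomes are assumptions. Over a wider grid (skill SD 0.5 to 1, subject-by-modality SD 0 to 0.5, up to 10 trials per cell), the rate without a subject term ran from 0.2% to 60%, while the subject-by-modality error term held 4.3 to 5.7%. The group and practice figures apply only under conditions that the plan does not state.

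**What to change.** In 4(e), replace the ANOVA wording with a named model:

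- Modality and weight as within-subject factors, with session or day included.
- Random terms for subject, subject-by-modality and subject-by-session.
- Participant group, if it is to be tested, judged against between-subject error.
- A mixed model rather than a classical repeated-measures ANOVA, because the number of days varies between subjects and the design is fractional.
- A form suited to counts or proportions for drops and breakages.

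For ratings compared across modality or weight, use a paired rank test on one value per subject and condition: Wilcoxon signed-rank for two conditions, Friedman for three where the data are complete. Keep Mann-Whitney only for comparisons between participant groups. Also state whether the modalities are balanced within each session and whether training-session trials are analysed.

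The cost is a few sentences and slightly more analysis work. Where subjects truly differ in response, apparent power on trial-level outcomes falls. With 12 subjects, three sessions, a difference of 0.3 and τ = 0.25, noncentrality is 12 × 18 × 0.045/2.125 = 4.57, and power is about 40% (simulated 37 to 39%) against about 60% with no subject term. The latter test has a false-positive rate of about 11%, so its extra power is not a real gain.
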